#### 4.4.5.2 iRECIST progression-free survival (iPFS)-Exploratory Objective

The immune Progression-Free Survival (iPFS) is defined as the time (months) from the first administration of APX005M to the event or censoring date.

$$iPFS \text{ (months)} = \frac{(date \text{ of event or censoring for iPFS}) - date \text{ of first APX005M dose}) + 1}{30.4375}$$

An event is defined as the first documentation of iCPD, clinical progression, or death due to any cause, whichever occurs earlier.

If subjects have iUPD which is confirmed at the next assessment as iCPD, then iPFS is the time from the first administration of APX005M to the first date of iUPD that is subsequently confirmed.

The rules for censoring cases are defined as follows:

If a subject is discontinued or lost to follow up before reporting an event will be censored at the last tumor assessment documenting the absence of PD.

Subjects who start other systemic anti-cancer therapy before reporting an event will be censored at the date of the start of this therapy.

Subjects who death or progress during the follow up period after  $\geq 2$  consecutive missed from the last tumor assessment visits will be censored at the date of the last evaluable tumor assessment before the tumor assessment of progressive disease or death.

The censoring and event date rules for Duration of Response are presented below.

**Table 7 Event and censoring dates for iPFS analyses**

Events scheme:

Scenario	Date of event
iUPD confirmed at the next assessment.	The first date of iUPD is subsequently confirmed.
If iUPD progression is not confirmed and there is no subsequent iSD, iPR, or iCR. The following scenarios may occur: 1.No further response assessments are done (Subject refusal, protocol noncompliance...). 2.The next timepoint response is iUPD, and iCPD never occurs.	The first date of iUPD is not subsequently confirmed.
Subject with non-objective progression but discontinuation of treatment by clinical progression.	Date of last tumor assessment Date of withdrawal discontinuation of treatment.
Death.	Date of death.

## Censoring scheme:

Scenario	Date of censoring
No tumor assessment after the baseline.	Date of the first dose.
iPD after 2 or more missed tumor assessments during follow up period.	Date of the last tumor assessment before the event.
No iPD and no Death.	Date of last tumor assessment documenting the absence of iPD. If last response is iSD with no previous iPD, date of end of treatment.
Receive any systemic therapy after treatment discontinuation.	Date of last tumor assessment documenting the absence of PD before starting systemic therapy

## 4.5 Safety Endpoints

Safety will be assessed by cohort through summaries of AEs, incidence and severity of AEs, laboratory test results, specific laboratory abnormalities grades according to NCI-CTCAE, ECG, vital signs, APX005M exposure, and premedication prior to APX005M.

### 4.5.1 Treatment

#### 4.5.1.1 Duration of treatment

The duration of treatment (in weeks) of each subject will be computed as:

$$\text{Duration of treatment(weeks)} = \frac{(\text{date of last dose} - \text{date of first dose of APX005M}) + (21 \text{ days (Cohort 1)} \text{ or } 14 \text{ days (Cohort2 or Cohort3)})}{7}$$

#### 4.5.1.2 Duration of treatment at starting dose

The duration of treatment (in weeks) at starting dose will be computed as:

$$\text{Duration of treatment at starting dose(weeks)} = \frac{(\text{date of last starting dose} - \text{date of first dose of APX005M}) + (21 \text{ days (Cohort 1)} \text{ or } 14 \text{ days (Cohort2 or Cohort3)})}{7}$$

\*Starting dose=0.3 mg/kg

#### 4.5.1.3 Dose intensity (DI)

Dose intensity (DI) is defined as the APX005M dose delivered per time unit and is expressed as mg/kg per week.

The weight registered for each cycle will be used to calculate the administered dose in mg/kg (in case a cycle's weight is missing it will be imputed via the LOCF –last observation carried forward– method).

#### 4.5.1.4 Relative dose intensity (RDI)

Relative dose intensity (RDI) is defined as the ratio of administered dose intensity to planned (reference) dose intensity, expressed as a percentage:

$$RDI (\%) = \frac{\text{Delivered dose intensity}}{\text{Target Dose Intensity}} * 100$$

#### 4.5.1.5 Number of cycles

The absolute and relative frequencies of the cycles administered per subject will be described. (Only cycles with doses greater than 0 are taken into account).

#### 4.5.1.6 Dose delay, interruptions, and reduction

Dose delays, interruptions, and reductions per subject and the reasons for these dose modifications will be described by subject. Information on delays and dose reductions reported in the study database will be considered.

## 4.5.2 Safety

### 4.5.2.1 Medical history, TEAEs and SAEs

TEAE is an AE occurs after administration of the first dose of the investigational product and through 30 days after the last dose of the investigational product, death, or initiation of new anticancer therapy, whichever occurs first.

SAEs, pregnancies, and TEAEs with potential immunologic etiology will be recorded up to 90 days after the last dose of investigational product, death, or initiation of new anticancer therapy, whichever occurs first. These SAEs / AEs will be considered TEAEs in the safety analysis.

In addition, the investigator should report any AEs that may occur after this period which are assessed to have a reasonable possibility of being associated with investigational therapy(ies). These AEs will be considered TEAEs in the safety analysis.

#### Notes:

- All AEs occurring after administration of first dose of investigational product will be considered as TEAEs in the analysis.
- If an AE date of onset is incomplete, an imputation rule will be used to classify the AE as treatment-emergent or not. The algorithm for imputing date of onset is provided in the section Handling of Missing Data.

Medical history: Events that occur after the subject signs the informed consent but prior to the first dose of APX005M will be recorded as past medical history.

### 4.5.2.2 Cytokine release syndrome / infusion reaction

Cytokine release syndrome/infusion reactions have been recorded as an adverse event.

In addition, all associated symptoms have been described as adverse events independently.

- For AE terms coded as "Cytokine release syndrome" or "Infusion reaction" it should be selected that it is not a symptom of a "Cytokine release syndrome" or "Infusion reaction".
- All the symptoms associated with each "Cytokine release syndrome" or "Infusion reaction" should be reported. For these symptoms, it has been indicated that it is a symptom of a "Cytokine release syndrome" or "Infusion reaction".

## 4.6 Other Derived Variables

In the case that more derived variables than the ones described in this document are required for the analysis, they will be defined and described in the statistical report.

## 5. GENERAL STATISTICAL METHODS

### 5.1 Sample Size

This is an exploratory Phase 2 study. Cohorts 1 and 2 will enroll 11 subjects each. Assuming a true response rate of about 18.2% (2 subjects with tumor response out of 11 subjects) in each of these cohorts, the estimated standard error of the response rate in each of these cohorts will be 11.6%. Cohort 3 will enroll 18 subjects. Assuming a true response rate in this cohort of about 16.7% (3 responders out of 18 subjects) the estimated standard error will be 8.8%.

### 5.2 Subject's Disposition

For subject study status, the number and percentage of subjects for each one of the following categories will be presented.

- Screened subjects, including screened failures (the number only)
- Screened-failure subjects (the number only)
- Enrolled subjects (the number only)
- Enrolled and treated subjects
- Subjects in Efficacy Population
- Subjects in Safety Population
- Subjects in Per protocol Population.
- Subjects who discontinued study treatment by primary reason
- Subjects who discontinued study by primary reason

For all categories of subjects, percentages will be calculated using the number of enrolled subjects.

The data for subject disposition, protocol deviation, eligibility, and whether a subject is included in the analysis populations will be listed.

End of treatment and end of study reasons will be displayed in a listing.

#### 5.2.1 Protocol Deviations

All protocol deviations will be collected separately from the clinical database. They will be recorded and categorized by the Pivotal study monitors in Danah, a specific clinical trial management system provided by Pivotal.

A listing of all patients with protocol deviations will be maintained by Pivotal and periodically reviewed by the Sponsor. The Sponsor may upgrade or downgrade the category of the protocol deviation, always based on the approved Deviation Plan.

All protocol deviations will be listed by category and deviation type.

The final list of protocol deviations will be reviewed before the database lock and provided to the biostatistician.

Some major deviations from the protocol that will potentially impact the primary efficacy objective and may lead to the exclusion of a subject from the per protocol population.

### 5.3 Summary of Statistical Methods

All subjects entered in the database will be included in subject data listings. The listings will be generally sorted by cohort and then Subject ID unless specified otherwise. All relevant subject data will be included in listings.

All applicable data will be summarized by cohort unless specified otherwise. In addition, data will be summarized by visit and/or time-point when appropriate. Unscheduled or repeat assessments will not be included in summary tables but will be included in listings.

Continuous variables will be summarized using the number of observations (n), the number of subjects with non-missing values, mean, standard deviation (SD), median, Q1, Q3, minimum, and maximum along with the total number of subjects contributing values.

Descriptive statistics for categorical/qualitative data will include frequency counts and percentages. The total number of subjects in the cohort (N) will be used as the denominator for percent calculations unless stated otherwise in the table footnote.

Time to event distributions (eg, PFS and DoR) will be estimated using the Kaplan-Meier methodology. In these analyses, in addition to the Kaplan-Meier curve, the median, Q1, Q3, and their corresponding CI 90% (if estimable), the number of events and censored cases distribution will be shown.

### 5.3.1 Demographics, Other Baseline Characteristics and Medication

Listings will also be presented for the demographic characteristics and disease history, respectively.

#### 5.3.1.1 Demographic Characteristics

The following variables for demographics characteristics will be summarized by cohort and overall:

- Gender (Male/ Female)
- Age (years)
- Race (American Indian or Alaska Native Asian/ Black or African American/ Native Hawaiian or other Pacific Islander/ White or Caucasian/Other) and Ethnicity (Hispanic or Latino/Not Hispanic or Latino/Unknown). Only categories with any occurrence will be listed.
- Height (cm) and weight (kg)
- ECOG performance status (0/ 1/ 2/ 3/ 4/ 5). Only categories with any occurrence will be listed.

#### 5.3.1.2 Disease characteristics

The following variables for disease history will be summarized by cohort and overall:

Subjects with disease prior to advance or metastatic disease.

For these subjects:

- Time (months) from the first biopsy of disease and diagnosis date of advanced or metastatic disease.

For all subjects

- Time (months) from diagnosis of advanced or metastatic disease and date of informed consent
- Histology (Superficial spreading malignant melanoma/Nodular malignant melanoma/Lentigo malignant melanoma/Acral lentiginous melanoma/Amelanotic melanoma/Oral/Mucosal/Skin-Limbs (upper)/Skin- Limbs (lower)/Skin- Trunk/Missing). Only categories with any occurrence will be listed.
- Histological grade (G1 – well differentiated/ G2 -moderately differentiated / G3 – poorly differentiated/ G4 -undifferentiated/ GX -grade cannot be assessed or Not Applicable /Missing). Only categories with any occurrence will be listed.
- Metastatic sites at study entry

Any metastatic sites at study entry? (Yes/No), in case of No a note will be included in the table footnote.

Subjects with a metastatic lesion at the time of study entry will be shown.

Specific metastatic sites

(Bone/ CNS/ Distant Lymph Nodes/ Liver/ Local or Regional Lymph Nodes/ Lung/ Skin or Subcutaneous/ Other)

- Unresectable/metastatic
- PD-L1 Status (Positive/Negative/Unknown)

### 5.3.1.3 Medical History

Medical history abnormalities will be coded to Medical Dictionary for Regulatory Activities (MedDRA) terms. The version used will be specified in the data display footnote.

The medical history will only be listed but not summarized.

### 5.3.1.4 Prior Systemic Therapy

A table with the maximum number of prior therapies by cohort will be summarized.

A table with the prior treatment regimen by cohort and by the number of lines will be summarized.

A table with the prior immunotherapy treatment by cohort will be summarized.

A listing will be provided for the Prior Systemic Therapy.

### 5.3.1.5 Prior Radiation

A listing will be provided for the Prior Radiation.

### 5.3.1.6 Prior Surgery

A listing will be provided for the Prior Surgery.

### 5.3.1.7 Prior and Concomitant Medications

Prior and concomitant medications will be listed in the same table but not summarized; a column will be included in the listing to indicate if the medication is prior or concomitant.

The premedication information will be included in the safety analysis.

### 5.3.1.8 Concomitant Procedures

A listing will be provided for the concomitant procedures performed.

### 5.3.2 Efficacy Analyses

#### 5.3.2.1 Primary efficacy endpoint (ORR by RECIST 1.1)

The primary efficacy endpoint is **ORR by RECIST 1.1**, as defined in [Section 4.4.2](#), is based on tumor assessments which will be performed by RECIST1.1 at Screening, about every 8 weeks during Treatment Phase.

The point estimate of the ORR will be presented along with an exact two-sided 90% confidence interval (CI) using the exact (Clopper-Pearson) method.

The ORR by RECIST 1.1 will be estimated for each cohort and overall.

In addition, swimmer, spider, and waterfall plots will be provided.

#### 5.3.2.2 Secondary efficacy endpoints:

**ORR** by iRECIST (and 90% confidence interval by exact distribution) will be estimated for each cohort and overall, as a secondary efficacy objective.

**DoR** will be estimated for each cohort and each tumor assessment method (by RECIST 1.1 and iRECIST). The DOR will be summarized using the Kaplan Meier method; the median event time (if appropriate) and two-sided 90%CI for the median will be provided.

The by-subject listings will be generated for the detailed tumor assessment, the response assessment by RECIST1.1 and iRECIST, and the derived DoR and PFS.

#### 5.3.2.3 Exploratory efficacy endpoints:

**PFS** will be summarized using the Kaplan-Meier method; the median event time (if appropriate) and two-sided 90%- CI for the median will be provided. The corresponding Kaplan Meier curve will also be presented.

PFS will be estimated for each cohort and overall either RECIST 1.1 and iRECIST criteria.

Note:

Pivotal will not perform the TFLs associated with the below exploratory objectives:

- Evaluate the association between potential tumor and blood biomarkers and antitumor activity and/or resistance
- Determine the presence and titre of anti-APX005M antibodies (ADA).

### 5.3.3 Safety Analyses

The population used for safety analyses will be the Safety Population.

Safety of APX005M will be assessed by cohort through summaries of TEAEs, the incidence, and severity of TEAEs, laboratory test results, specific laboratory abnormalities grades according to NCI-CTCAE, ECG, vital signs, APX005M exposure, and premedication administered prior to APX005M.

#### 5.3.3.1 Treatment Exposure and pre-medication

##### 5.3.3.1.1 APX005M

Exposure of the APX005M will be summarized by cohort and overall. The following variables will be summarized:

- Maximum number of cycles started (Mean, SD, Median, Q1, Q3, Min and Max)
- Number of subjects who started the maximum cycle of 1, 2, 3, 4, and so on (number and percentage)
- Duration of treatment (weeks) (Mean, SD, Median, Q1, Q3, Min and Max)

The following variables will be summarized by cohort and overall.

- Number of infusions administered per subject (Mean, SD, Median, Q1, Q3, Min and Max)
- Number of subjects with dose reductions (number and percentage)
- Number of subjects with dose interruptions (number and percentage)
- Number of subjects with dose delivered off schedule (number and percentage)

In addition, the following variables will be summarized in the APX005M exposure table mentioned above.

- Dose intensity (mg/kg/week) (Mean, SD, Median, Q1, Q3, Min and Max)
- Relative dose intensity (%) (Mean, SD, Median, Q1, Q3, Min and Max)

Treatment assignment will be listed by subject, a listing of APX005M infusion information will be provided per subject and cycle.

The maximum number of cycles started, duration of treatment(weeks), and total dose will be listed per subject.

In addition, a separate listing will be provided for the pre-medications prior to the administration of investigational products.

##### 5.3.3.1.2 Radiotherapy

Subjects included in cohort 3 receive treatment with radiotherapy.

- Maximum number of cycles started (Mean, SD, Median, Q1, Q3, Min and Max)
- Number of subjects who started the maximum cycle of 1, 2, 3, 4, and so on (number and percentage)
- Duration of treatment (weeks) (Mean, SD, Median, Q1, Q3, Min and Max)
- Total dose administered. (Mean, SD, Median, Q1, Q3, Min and Max)

In addition, a separate listing will be provided for the date of the session time of session and dose per cycle and subject.

### 5.3.3.2 Treatment Emergent Adverse Events

All TEAEs will be coded to System Organ Class (SOC) and Preferred Term (PT) using the MedDRA dictionary v24.0. or later.

Related Adverse Events to APX005M: adverse events with relationship to study treatment (as recorded on the AE eCRF page, Relationship with APX005M = Related) reported by the investigator and those of missing or unknown relationship.

Related Adverse Events to Radiotherapy: adverse events with relationship to radiotherapy (as recorded on the AE eCRF page, Relationship with Radiotherapy = Related) reported by the investigator and those of missing or unknown relationship.

Serious Adverse Events (SAE): serious adverse events (as recorded on the AE eCRF page, Serious Adverse Event = Yes).

Adverse Events Leading to Treatment Discontinuation: adverse events leading to permanent discontinuation of study treatment (as recorded on the AE eCRF page, Action taken with study treatment = Drug withdrawn).

Adverse Events Leading to Death: adverse event leading to death (as recorded on the AE eCRF page, Outcome = Fatal, as well as AEs of Grade 5).

Immune mediated Adverse Events: immune mediated adverse events (as recorded on the AE eCRF page, Immune mediated adverse event= Yes).

Infusion Reactions and or Cytokine Release Syndrome: are identified based on an AE term coded as 'Cytokine release syndrome' or 'Infusion Reaction'

The constellation of symptoms that comprise an APX005M infusion related reaction or cytokine release syndrome will be described.

The NCI-CTCAE version 4.03 will be used to assess the severity grade of TEAEs.

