5.2 Adverse Event Classification

5.2.1 Relationship to Investigational Therapy(ies)

The Investigator will assign attribution of the possible association of the event with use of the investigational therapy(ies) (APX005M and/or radiation), and this information will be entered into electronic data capture (EDC) system using the classification system listed below:

Related to Investigational Therapy(ies)

The event is suspected to be related if:

- There is a clinically plausible time sequence between the AE onset and administration of investigational therapy(ies)
- There is a biologically plausible mechanism for the investigational therapy(ies) to cause or contribute to the AE
- The event improves or diminishes upon temporary interruption of the investigational therapy(ies) without the initiation of any specific treatment for the event (dose delay) and/or recurs or worsens when resuming treatment after criteria for retreatment are met
- The AE cannot be reasonably attributed to concurrent or underlying illness, other drugs, or procedures

Apexigen Medical Monitor (or designee) will review all Investigator-reported assessments of relationship and confirm.

Unrelated to Investigational Therapy(ies)

The event is not suspected to be related if:

- The AE is more likely to be explained by the subject's underlying disease, clinical state, concomitant medical, or study or non-study procedure
- The time occurrence of the AE is not reasonably related to administration of investigational therapy(ies)
- The event is not related to the investigational therapy(ies)

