### 5.3.3.2.1 TEAEs – Overview

An overall summary table will be provided showing the number of TEAEs, the number, and proportion of subjects who presented:

- Any TEAE.
- Any TEAE grade 3 or higher.
- Any TEAE grade 3.
- Any TEAE grade 4.
- Any TEAE grade 5.
- Any TEAE related to APX005M.
- Any TEAE related to APX005M grade 3 or higher.
- Any TEAE related to APX005M grade 3.
- Any TEAE related to APX005M grade 4.
- Any TEAE related to APX005M grade 5.
- Any TEAE related to APX005M only
- Any TEAE leading to dose reduction (APX005M).
- Any TEAE leading to dose delay (APX005M)
- Any TEAE leading to treatment interruption (APX005M)
- Any TEAE leading to treatment discontinuation (APX005M).
- Any TEAE related to Radiotherapy (applicable to Cohort 3)
- Any TEAE related to Radiotherapy only (applicable to Cohort 3)
- Any TEAE leading to radiation discontinuation (only applicable in Cohort 3)
- Any TEAE Immune Mediated.
- Any TEAE Infusion reaction/ cytokine release syndrome.
- Any Serious TEAE.
- Any Serious TEAE with a fatal outcome.
- Any Serious TEAE related to APX005M.
- Any Serious TEAE related to APX005M with fatal outcome.
- Any Serious TEAE related to APX005M only
- Any Serious TEAE related to Radiotherapy (applicable to Cohort 3)
- Any Serious TEAE related to Radiotherapy only (applicable to Cohort 3)

This information will be presented by cohort and overall.

Separate listings will be produced for:

- TEAEs
- TEAEs excluding events marked as a symptom of CRS/IRR
- Serious TEAEs
- TEAEs leading to APX005M discontinuation
- TEAEs leading to APX005M delay
- TEAEs leading to APX005M reductions
- TEAEs leading to infusion interruption
- TEAEs with fatal outcome
- TEAEs immune-mediated events
- TEAEs marked as a symptom of CRS / IRR

The listings will be sorted by Subject ID.

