#### TEAEs relationship

If relationship is missing or unknown, the event will be listed as missing or unknown relationship but summarized as related.

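### The rule that counts a missing radiotherapy relationship as related is not limited to Cohort 3, so blank fields in Cohorts 1 and 2 would wrongly reduce the two APX005M-only adverse event rows

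*SAP*

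**What the plan says.** SAP 5.3.3.2 counts as related to radiotherapy the events with "Relationship with Radiotherapy = Related) reported by the investigator and those of missing or unknown relationship". SAP 5.3.6 gives the general imputation rule: "If relationship is missing or unknown, the event will be listed as missing or unknown relationship but summarized as related". Neither place mentions a cohort, and neither separates a missing entry from one that does not apply.

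SAP 5.3.3.1.2 states who is irradiated: "Subjects included in cohort 3 receive treatment with radiotherapy". Cohorts 1 and 2 receive APX005M alone (SAP 2.3).

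The overview table in SAP 5.3.3.2.1 has 27 rows. Its four radiotherapy-relationship rows carry a cohort limit, for example "Any TEAE related to Radiotherapy (applicable to Cohort 3". The rows "Any TEAE related to APX005M only" and "Any Serious TEAE related to APX005M only" carry none. Of the table as a whole the SAP says "This information will be presented by cohort and overall". The word 'only' is not defined. The table shells are in a separate document (SAP 7).

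**The concern.** The two APX005M-only rows are meant to isolate events attributed to the drug and not to radiation. To derive them, the program must consult the radiotherapy relationship in every cohort, including the two in which no radiotherapy was given. In those two cohorts every APX005M-related event should qualify, because there is no other study treatment to blame. The written rule can give the opposite result: an empty radiotherapy field is turned into a positive attribution to radiation, and the event leaves the APX005M-only row.

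At stake are two descriptive safety rows, one of them for serious events, and their overall column. Safety of APX005M alone or with radiation in each cohort is a secondary objective, so these rows are likely to be read. A partial loss would be harder to notice than a complete one, because the count would be too low without looking impossible.

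**Working it through.** The documents give no figure on this point, so there is none to reproduce. The check applies the written rule to possible records and then sizes the effect.

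**Inputs**
- Missing or unknown counts as related, with no cohort limit: SAP 5.3.3.2 and 5.3.6.
- The APX005M-only rows are shown for all cohorts and overall: SAP 5.3.3.2.1.
- Radiotherapy is given in Cohort 3 only: SAP 2.3 and 5.3.3.1.2.
- Planned sizes are 11, 11 and 18: SAP 5.1.
- Assumption: 'only' means related to APX005M and not related to radiotherapy.

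**Step 1: classification.** Let R(x) be true when x is related, missing or unknown. Then APX005M-only = R(APX005M) and not R(radiotherapy). For an event whose APX005M relationship is related:

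| Radiotherapy field | R(radiotherapy) | In APX005M-only row? |
|---|---|---|
| Not related | false | yes |
| Not applicable (own code) | false | yes |
| Blank or unknown | true | no |
| Related | true | no |

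Take a Cohort 1 subject with cytokine release syndrome, APX005M relationship related, radiotherapy field blank. The event is classed as related to both treatments and is excluded, although APX005M was the only study treatment.

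**Step 2: size.** If a fraction f of the APX005M-related events in Cohorts 1 and 2 has a blank field, the event count in the row falls by f, anywhere from 0 to 100%. A subject drops out only when all of that subject's APX005M-related events are blank, so subject counts can fall less. As an illustration, assume that all 11 subjects in a cohort have m APX005M-related events each, and that each event is blank independently with probability q. The expected number of subjects left in the row is 11 × (1 − q^m):

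| m | q = 0 | q = 0.25 | q = 0.5 | q = 0.9 | q = 1 |
|---|---|---|---|---|---|
| 1 | 11 | 8.25 | 5.5 | 1.1 | 0 |
| 3 | 11 | 10.83 | 9.62 | 2.98 | 0 |
| 5 | 11 | 10.99 | 10.66 | 4.5 | 0 |

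Only q = 1 gives 0 of 11. If blanks are all-or-none within a subject, the m = 1 line applies whatever m is.

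**Step 3: reach.** Cohorts 1 and 2 are (11 + 11)/(11 + 11 + 18) = 22/40 = 55% of planned subjects. This is their share of the overall column, not a share of events lost. In the fully blank case the overall entries for these two rows would come from Cohort 3 alone. Two of the 27 overview rows are exposed.

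**Step 4: after the change.** With the field set to not applicable in Cohorts 1 and 2, R(radiotherapy) is false there. The APX005M-only row then equals the APX005M-related row, up to 11 of 11 in each cohort.

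**The case against.** The effect depends on how a data field is completed, and the case report form is not among the documents. Protocol 5.2.1 asks the investigator to attribute each event to "use of the investigational therapy(ies) (APX005M and/or radiation" and offers two categories, related and unrelated. For a subject who was never irradiated the natural entry is unrelated, and if sites enter that, nothing is lost. The SAP also already treats this attribute as specific to Cohort 3 in every radiotherapy-relationship row and table. It could therefore be argued that 'missing' was meant as expected but not supplied, and the external shells may say so. A zero beside a non-zero APX005M-related count would also be an obvious error, and the listings show the relationship as missing rather than imputed.

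Most of this stands as a limit on the harm, but it does not remove the gap. Blanks are plausible:
- The minimum adverse event data in Protocol 5.3.1 name the relationship to APX005M and do not name radiotherapy.
- Cohort 3 was introduced by Amendment 2, dated 28 December 2020, about a year after the first subject was enrolled on 16 December 2019 (SAP 5.3.8). That early records lack a radiotherapy attribution is an inference, not a documented fact.
- Nothing in the documents tells sites what to enter in Cohorts 1 and 2.

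The SAP rule as written has one literal reading, and a programmer may follow it.

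**Conclusion.** The rule is too broad as written. It can give a wrong result in two descriptive overview rows and in their overall column. The loss in Cohorts 1 and 2 lies between nil and complete, and the documents do not narrow that range. The finding rests on the stated reading of 'only' and on at least some radiotherapy fields being blank or unknown in those cohorts.

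A reader might infer more, and the documents do not support it:
- **That Cohorts 1 and 2 will show zero.** This needs every APX005M-related event there to have a blank or unknown field, which is not shown.
- **That monotherapy events will be reported as radiotherapy-related.** The rows and tables for radiotherapy relationship are limited to Cohort 3.
- **That the comparison of drug-alone with combination safety is reversed.** The objective is safety within each cohort, and no between-cohort safety comparison is specified. The APX005M-related rows, the tables by system organ class and preferred term, and the related serious event tables stay correct. So does every efficacy endpoint.
- **That the Cohort 3 derivation is also wrong.** Counting a missing relationship as related is a conservative choice where radiotherapy is given, and nothing here shows it to be in error.

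This is a minor point, worth settling before the tables are programmed.

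**What to change.** In SAP 5.3.3.2 and 5.3.6:
- Apply the rule that a missing or unknown radiotherapy relationship counts as related to Cohort 3 only.
- In Cohorts 1 and 2, set the radiotherapy relationship to not applicable, handled as not related.
- Define the APX005M-only category as related to APX005M and not related to radiotherapy, and state that in Cohorts 1 and 2 it therefore equals the APX005M-related category.

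Leave the Cohort 3 derivation unchanged. A further condition that a fraction was delivered before event onset is not needed here. It would add a date comparison that meets the day-15 imputation of partial dates.

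The cost is a sentence or two in the SAP and a cohort condition in the derivation code. If the case report form already prevents blanks, no result changes.
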